### 6.4.3 Calculation of number needed to treat

The number needed to treat (to benefit) will be calculated using the method of Altman and Andersen (Altman and Andersen 1999) for each dose for different durations of treatment as

$$\text{NNT (t)} = 1 / [ S_{\text{placebo(t)}}^{\text{hazard ratio for dose versus placebo}} - S_{\text{placebo(t)}} ]$$

using  $S(t)$  calculated as described in section 6.4.1. It will be extrapolated as described by Altman and Andersen to the 5 year timepoint from the timepoint of follow-up achieved by 10% of patients across all trial arms and trial parts  $T_{10\%}$  under the assumption of approximately constant event rates and benefit as

$$\text{NNT (5 years)} = ( T_{10\%} / 5 \text{ years} ) \times \text{NNT (} T_{10\%} \text{)}.$$

3 year and 1 year NNTs will be calculated and it is expected that this can be done without such an extrapolation unless the study is stopped an interim analysis. Confidence intervals with appropriate coverage probabilities will be calculated using Bootstrap methods.

## 6.5 Methodology for dose response evaluation

Dose-response estimation will be performed to support the evaluation of a number of endpoints as indicated in the protocol, among them the hazard ratios derived from the analysis of the primary endpoint.

[figure not shown]
Dose-response estimation will be done using parametric dose-response modelling as described in Pinheiro et al. (2014) combined with model averaging techniques (see Bornkamp et al. 2015). The model averaging approach will use a weighted subset of seven possible parametric models as the estimate of the dose response. The parametric models are a linear model, a quadratic model, a model linear in log dose, an emax model, a sigmoid emax model, an exponential model, and a beta model as implemented in the R package DoseFinding. The model averaged dose response and confidence intervals will be derived from a parametric bootstrap. In addition, comparisons between doses will also be derived with their corresponding confidence intervals.

The time to event endpoints analyzed using the general approach as described in Pinheiro et al. (2014) will use the estimated hazard ratios and covariance matrix derived from a parametric regression model for survival endpoints for which the treatment estimates are given a proportional hazards model. Estimates for the analysis of other endpoints will be derived from fitting models that account for measurements collected over time whenever applicable. [REDACTED]

The estimation of the dose response will be based on the methods described in Pinheiro et al. 2014 as a more general framework for the derivation of dose responses when the response is any form of derived statistic for the dose groups with their corresponding variance covariance matrix. The derived dose response will be obtained from a model that is the average of at least three of fitted models of dose response where the weights will used the generalized AIC

measure as described in Pinheiro et al 2014. The corresponding mean dose response curve and its confidence intervals will be derived from a parametric bootstrap procedure also described in the same reference.

**Figure 6-6 Candidate dose response patterns**

## 7 Safety evaluation

Safety will be evaluated based on the safety set (SAF). The assessment of safety will be based primarily on the assessment of potential and identified risks defined in the risk management plan (RMP), the frequency of adverse events, laboratory abnormalities, and serious adverse events suspected by the investigators to be related to study treatments. Other safety data (like vital signs, ECG) will be summarized as appropriate.

Selected safety analyses will be based on looking at events and variables recorded while patients were still on investigational drug (i.e. data will be considered censored at the latest one quarter year + 28 days = 119 days after the last study injection, and up -to/including the EOS visit of the core phase), as supportive analyses.

Since the study is intended to be the only pivotal trial in the regulatory submission, selected key safety analyses including disposition, demographics, exposure, adverse events, serious adverse events, key outputs for adverse events of special interest, deaths, laboratory abnormalities and laboratory values over time will be repeated for those groups specified in [table 2.3-2](#).

Selected safety analyses will also be shown by time period (from randomization to  $\leq 3$  months post-randomization,  $> 3$  to  $\leq 6$  months,  $> 6$  to  $\leq 9$  months,  $> 9$  to  $\leq 12$  months,  $> 12$  months to the end of core study visit) to evaluate any changes in safety during more short-term and longer term treatment.

## 7.1 Safety assessment approach accounting for multiplicity

No adjustments for multiplicity will be made for safety assessments. Adjustments will be made for multiplicity of the primary and key secondary efficacy endpoints, as described earlier in this document.

## 7.2 Statistical models used in multiple safety contexts

Safety data will be summarized across the two trial parts and the two randomization plans in trial part 2, both of which might influence safety reporting as described in [section 2.4](#).

For this purpose hazard ratios versus placebo will be estimated for binary safety outcomes (e.g. at least one occurrence of adverse events) using Cox regression stratified for time since index MI and trial part. Time to event methods have been chosen over relative risk regression or logistic regression to account for differential follow-up. This can be implemented using SAS code similar to the following:

```
proc phreg data=dataset;
  class treatment(ref="Placebo") <time since index MI>
    <trial part>;
  model time*event(0) = treatment / ties=exact risklimits;
  strata <time since index MI > <trial part>;
run;
```

Trial part by treatment interactions will be investigated. For selected events, additional predictive baseline covariates may be added to the model, namely age, sex, race, region and other event specific variables. As summary statistics patients with an event per 100 patient years of follow-up (defined as follow-up to first event or censoring) will be reported.

Rates of multiple occurrences of safety events will be compared between treatment groups for selected safety events of special interest, where such an analysis is of interest. A Negative Binomial regression including terms for treatment, trial part, and log (time at risk) as offset variable will be used. This model was chosen, because the number of recurrent events in a population will follow a negative binomial distribution if there is a distribution of different individual Poisson event rates in the population that follows a gamma distribution ([Glynn et al. 1993](#)) ([Glynn and Buring 1996](#)). While the population distribution may not exactly follow a gamma distribution, the maximum likelihood estimation of the additional dispersion parameter compared to the Poisson distribution from the data allows the negative binomial model approximate the data in this respect and to capture the extent of unexplained heterogeneity in the population. The logarithm of the time at risk is used as an offset (i.e. as a covariate with coefficient 1), because a log link function is used in order to effectively analyze the rate of events per time unit. The following SAS code illustrates the statistical model and methods intended for this analysis:

```
PROC GENMOD DATA=events;
  CLASS treatment(ref='Placebo') <trial part & time since index MI>;
  MODEL <number of events> = treatment
    <trial part & time since index MI> / OFFSET=<log time at risk>
```

```
DIST=NB LINK=LOG LRCI;  
RUN;
```

As matching summary statistics, events per 100 patient years of follow-up will be reported. For selected events, additional potentially predictive covariates will be added to the model, namely at least age, sex, race and region. When selecting repeated events it has to be ensured that a single adverse event case report form entry is only counted once (e.g. by ensuring only one record per adverse event sequence number is counted), as analysis dataset may contain multiple records for one CRF report to allow identification via e.g. different SMQs.

When such a model is used for specific adverse events of interest and a sufficient number of events to make this display useful is available, these data will also be displayed graphically as events per unit time of follow-up for different time intervals (e.g. first 6 months, 6 months – 1 year, 1 year to 2 years ... or smaller time intervals as appropriate) using meaningful categories of time to show time patterns of event occurrence and potential changes in treatment effect over time. Measures of uncertainty will be provided, as well as information on the extent of overdispersion / population heterogeneity.

Changes from baseline in continuous safety parameters will be plotted over time based on both trial parts using repeated measures mixed model. The following SAS code illustrates the statistical model and methods intended for this analysis:

```
proc mixed data=dataset;  
  class patient visit treatment <trial part>  
    <time since index MI>;  
  model <change from baseline> = treatment visit treatment*visit  
    baseline <trial part>  
    <time since index MI>  
    / s ddfm=kr;  
  repeated visit / subject = patient type = un;  
run;
```

with appropriately transformed values. Comparisons of each dose to placebo at each visit will be conducted if feasible. Additional analyses will add potentially predictive covariates, namely age, sex, race, region, education, exercise level, alcohol use, smoking history, BMI and hypertension to the model. The following variables will be analyzed on the log-scales and results will be back-transformed to report geometric means and ratios of geometric means versus placebo:

- [REDACTED]
- ALT (SGPT), AST (SGOT), total bilirubin, direct bilirubin, alkaline phosphatase
- Triglycerides, HDL, LDL, VLDL
- hsCRP

All other safety variables will be analyzed without any transformation based on the arithmetic mean and differences in arithmetic means versus placebo.

Panel plots of the results of these analyses showing means/geometric means or differences in means/ratios of geometric means over time will be made available for the clinical study report. 95% pointwise confidence intervals will be provided to allow judgment on the variability in the underlying data, but due to the obvious multiplicity issues consideration of these confidence intervals or p-values from the model described above cannot form the basis of any formal inference.

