5.2 Treatment arms

Following protocol Amendment 6 patients will be assigned to one of the following 4 treatment arms in a ratio of 1.4 : 1.3 : 1.3 : 2

- Canakinumab 50 mg s.c. at randomization (month 0), placebo s.c. at week 2 (month 0.5) , 50 mg s.c. at week 12 (month 3) and thereafter 50 mg s.c. quarterly
- Canakinumab 150 mg s.c. at randomization (month 0), placebo s.c. at week 2 (month 0.5), 150 mg s.c. at week 12 (month 3) and thereafter 150 mg s.c. quarterly
- Canakinumab 300 mg s.c. at randomization (month 0), week 2 (month 0.5) , week 12 (month 3) and thereafter 300 mg s.c. quarterly
- Placebo s.c. at randomization (month 0), week 2 (month 0.5) , week 12 (month 3) and thereafter placebo s.c. quarterly

with allocation in a 1.3 : 0.7 : 1 ratio to 300 mg, 150 mg and placebo respectively in randomization plan A and 0.6 : 1.4 : 1 to 150 mg, 50 mg and placebo respectively in randomization plan B. All patients will be equally likely to be assigned to randomization plan A or B. Within each of the two randomization plans patients will have a 2:1 probability of being on active treatment. Prior to protocol amendment 6, patients were assigned in a 1:1:1

ratio to the 300 mg arm, the 150 mg arm or placebo. Across trial parts 1 and 2 this will approximately result in a 1:1:1:1.5 allocation to 300, 150, 50 mg and placebo, respectively. More precisely, given about 743 patients in trial part one and 9257 in trial part 2, the overall patient allocation would be approximately 2253 for both the 300 and 150 mg groups, 2160 for the 50 mg group and 3333 for the placebo group (a 1.01:1.01:0.97:1.5 ratio).

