As far as combining data from trial part 1 and trial part 2 is concerned, the pre-specified analysis preserves the double-blind nature of the contrast in the same way that a patient-level (network) meta-analysis would. This is done by not making any direct comparisons between patients in trial part 2 and those in trial part 1 - i.e. no naïve pooling of patients across trial part, which would have been inappropriate, because patients were not concurrently recruited for the two trial parts and assignment to trial part was not at random. Instead, for example the 50 mg dose in trial part 2 can only be compared to the placebo group in trial part 1 indirectly using a double contrast by combining the 50 mg versus 300 mg and 50 mg versus 150 mg contrasts in trial part 2 with the 300 mg versus placebo and 150 mg versus placebo contrasts in trial part 1. As discussed by Senn, estimates obtained in this way have a substantially higher variance than the direct single (potentially biased) contrast ([Senn 2008](#)). Comparisons between treatments randomized to Part II on the other hand pool all concomitantly randomized arms because the potential bias is considered to be too small to justify the loss in efficiency incurred by such an approach. Furthermore, it was decided that any hypothetical bias could be handled for several reasons. Firstly, because patients are randomly assigned to the two randomization plans, one can expect patients in randomization plan A and B to be comparable at baseline. Secondly, any possible bias is expected to be small, if it exists. While investigators and patients can potentially identify whether patients are either on 300 mg, 150 mg, or placebo (trial part 1 or randomization plan A in trial part 2) or alternatively on 150 mg, 50 mg, or placebo (randomization plan B in trial part 2), the odds of a patient being on active treatment are the same in either case (2:1). In either case the number of potential treatment groups is only narrowed down to a limited extent, namely from 4 to 3. Taken together, this makes it unlikely that any influence of this knowledge on investigators and patients would have any substantial impact with respect to e.g. patient management, follow-up or endpoint

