### 6.4.1 Overall Kaplan-Meier type graphs across trial parts

A Cox model stratified for treatment group (placebo, 50 mg, 150 mg or 300 mg) and time since index MI (< 6 months, ≥ 6 months), with trial part as a covariate will be used to obtain Breslow estimates ([Breslow 1974](#)) for the predicted survival curves for each combination of treatment group, time since index MI and trial part – including for the 50 mg group in trial part 1. These predicted survival curves will then be aggregated for an appropriate cohort of patients within each of the 4 treatment groups to obtain a single overall Kaplan-Meier type graph for the 4 treatment groups.

The use of a Cox model stratified for treatment group (placebo, 50 mg, 150 mg or 300 mg) – and also time since index MI (< 6 months, ≥ 6 months) – is a suggestion by Zhang et al. ([Zhang et al. 2007](#)) and [name] ([personal communication, 2011](#)). As pointed out by Zhang et al. such a model makes no assumption of proportional hazards between treatment groups or time since index MI groups. Thus, it is more appropriate for obtaining a graphical representation that allows an inspection of the relative effectiveness of treatment groups over time. Using trial part as a covariate and assuming the same proportional effect of trial part for the whole follow-up period for each of the 8 strata (treatment group / time since index MI)

allows extrapolation of what a 50 mg group in trial part 1 would have been like, as suggested by [name] ([personal communication, 2011](#)). To assess the assumptions involved the predicted survival curves from this model for the placebo, 150 mg and 300 mg groups in each stratum and for the 50 mg group in all trial part 2 strata will be compared graphically to those from a model that treats trial part as an additional stratification variable. Should the assumption be strongly violated with respect to trial part having a constant effect over time, it would be an alternative to assume a trial part effect that is only proportional over specific time intervals (e.g. up to 90 days, day 91 to day 183, days 184 to 1 year, 1 year to 2 years, > 2 years).

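### The repeated-measures safety model lets treatment but not trial part vary by visit, so late 50 mg versus placebo laboratory contrasts are biased if the two parts diverge over follow-up

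*SAP*

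**What the plan says.** SAP 7.2 pools the parts for this analysis: "Changes from baseline in continuous safety parameters will be plotted over time based on both trial parts using repeated measures mixed model". The fixed effects begin "model <change from baseline> = treatment visit treatment*visit" and continue with "baseline <trial part>" and time since index MI, none of them crossed with visit. The covariance is unstructured ("repeated visit / subject = patient type = un"). The reported contrasts are per visit: "Comparisons of each dose to placebo at each visit will be conducted if feasible". The same section says that the resulting intervals and p-values cannot support formal inference, because of multiplicity.

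Elsewhere the plan keeps the parts apart. SAP 2.4 describes the pre-specified analysis as "not making any direct comparisons between patients in trial part 2 and those in trial part 1". The Cox safety models in SAP 7.2 are stratified by trial part. Protocol 9.5.3 wants risk and ratio measures of safety to account for trial part, so that differential follow-up or differing populations do not confound them. For the overall Kaplan-Meier type graph, SAP 6.4.1 starts from a constant part effect but plans a graphical check and offers an alternative: "Should the assumption be strongly violated with respect to trial part having a constant effect over time". No check or alternative is given for the mixed model. The investigation of trial part by treatment interaction in SAP 7.2 belongs to the Cox model and does not involve visit.

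**The concern.** SAP 6.4 notes that one arm is absent from Part 1, and SAP 6.4.1 notes that length of follow-up differs between the parts by design. At the latest visits the 50 mg data come only from Part 2, while placebo is an increasing mixture of both parts. The model can correct for that mixture only through a single shift common to all visits. If the gap between parts widens or narrows during follow-up, the uncorrected remainder has nowhere to go except the treatment-by-visit terms.

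At stake is the reading of the long-term laboratory panels (lipids, liver tests, hsCRP and others). A late 50 mg difference from placebo, or a late dose gradient, could partly reflect which part the patients came from. SAP 7 counts laboratory values over time among the key safety analyses of what is intended to be the only pivotal trial in the submission.

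**Working it through.** **1. The plan's allocation.** Protocol 5.2 works from "given about 743 patients in trial part one and 9257 in trial part 2". Part 1 (1:1:1) gives 743/3 = 247.7 per arm. Part 2 gives 9257 × 1.3/6 = 2005.7 for each of 300 mg and 150 mg, 9257 × 1.4/6 = 2160.0 for 50 mg and 9257 × 2/6 = 3085.7 for placebo. The totals are 2253, 2253, 2160 and 3333, as the protocol states. Part 1 is therefore 247.7/3333.3 = 7.4% of placebo, 247.7/2253.3 = 11.0% of 150 mg and of 300 mg, and 0% of 50 mg.

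**2. Part 1 share at late visits.** The duration of about 72 months is from Protocol 3.1. The rest is assumed: uniform accrual, Part 1 over the first L months, Part 2 from L to month 36, administrative censoring only. A patient reaches visit month v if enrolled by month 72 − v, so for v ≥ 36 the Part 1 share of placebo is

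s(v) = 247.7 / [247.7 + 3085.7 × (72 − v − L)/(36 − L)].

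With L = 6: month 42, 247.7/(247.7 + 3085.7 × 24/30) = 9.1%; month 54 (12/30), 16.7%; month 60 (6/30), 28.6%. With L of 9 to 15 months the month 54 share is 19 to 36%.

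**3. How it enters the contrast.** Let d(v) be the Part 1 minus Part 2 difference at visit v and g the single fitted shift. Ignoring borrowing across visits, the error in 50 mg minus placebo is about −s(v) × [d(v) − g]. It is zero when d is constant. Example: L = 6, d rising linearly from 0 to 1 SD by month 60, compound symmetry. The full fit's early error of +0.028 implies g ≈ 0.028/0.074 = 0.38. At month 60 the formula gives −0.286 × (1 − 0.38) = −0.18; the full fit gives −0.186.

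**4. Full fit.** Expected-value generalized least squares, no drug effect, residual SD 1, known correlation (compound symmetry 0.5 or autoregressive 0.7), L = 3, 6 or 12 months, time since index MI omitted, drift of 1 SD by month 60:

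| Month | Part 1 share of placebo | Error, 50 mg − placebo (SD) | Standard error (SD) |
|---|---|---|---|
| 0.5 | 7.4% | +0.025 to +0.030 | 0.028 |
| 36 | 7.4% | −0.014 to −0.019 | 0.028 |
| 42 | 9 to 10% | −0.023 to −0.036 | 0.029 to 0.030 |
| 48 | 11 to 14% | −0.037 to −0.068 | 0.032 to 0.035 |
| 54 | 15 to 24% | −0.058 to −0.142 | 0.035 to 0.045 |
| 60 (L = 3 or 6) | 23 to 29% | −0.096 to −0.186 | 0.042 to 0.050 |

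The error is proportional to the drift. At month 54 the drift reached is 54/60 = 0.9 SD, so the error is 0.058/0.9 = 6% to 0.142/0.9 = 16% of it; at month 60 it is 10 to 19%. A separate simulation with slower Part 1 enrolment (9 to 15 months) and a drift of 0.3 SD by month 54 gave −0.03 to −0.06 SD there, or 10 to 20%.

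Scaled to a 0.3 SD final drift, the error is −0.007 to −0.011 SD at month 42 and −0.029 to −0.056 SD at month 60 (0.6 to 1.2 standard errors). For 0.25 SD it is −0.024 to −0.047 SD at month 60 (0.5 to 1.0 standard errors). The 150 mg contrast moves the other way because its Part 1 share is larger: +0.035 to +0.062 SD at the last visit per 1 SD of drift, or +0.01 to +0.02 SD for 0.3 SD. The 300 mg arm has the same allocation.

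**5. With trial part by visit added.** The expected error is 0 at every visit. The standard error at month 60 (L = 6, compound symmetry) goes from 0.047 to 0.048 SD.

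**6. Baseline.** If the baseline slope changes over visits but baseline means are equal in the two parts, the error is 0. With Part 1 baseline assumed 0.25 SD higher it is 0.007 to 0.014 SD at the last visit. The usual cost is precision: if the correlation with baseline falls from 0.8 to 0.5, a common slope is off by 0.15 at each end. That adds 0.15² = 0.0225 to a residual variance of 1 − 0.8² = 0.36 early (6%) or 1 − 0.5² = 0.75 late (3%).

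**The case against.** The case against giving this much weight is good, and most of it stands. A stable difference between parts, the simplest form of population or care difference, is already removed by the main effect. Part 1 is only 7.4% of placebo until follow-up thins out, so only the last, sparse visits are exposed. Accrual, correlation and drift are all assumed, and the calculation treats the covariance as known although the SAP estimates it without structure. A constant part effect is also a common default in this plan: the negative binomial models use one, and SAP 6.4.1 starts from one. The code is offered as an illustration, comparisons depend on feasibility, and laboratory safety also rests on shift tables, notable-value frequencies and hepatic threshold tables that do not use this model.

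Three stronger readings do not survive. A reader might infer that a part difference changing over follow-up is the SAP's own reason for keeping the parts apart. Protocol 9.1 and 9.4.2 and SAP 2.4 and 6.3.1 give a different reason: recruitment was not concurrent, so populations or background care may differ. A reader might also infer that the constant baseline slope mixes the parts; step 6 shows that it is essentially a matter of precision. Finally, a rule against reporting 50 mg at visits with no 50 mg data might seem necessary. It is not, since that contrast cannot be estimated and the SAP limits comparisons to feasible ones.

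What remains is that this model is specified nowhere else, the per-visit contrasts go into the study report with 95% intervals, and those intervals do not reflect this error. The SAP's caveat concerns multiplicity, not confounding.

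**Conclusion.** The point holds as a conditional and minor one. If the difference between trial parts changes over follow-up, the late-visit 50 mg versus placebo contrasts and the apparent dose pattern in the descriptive laboratory plots are biased. Under the assumed accrual the bias is negligible before about month 42. At months 54 to 60 it is roughly 10 to 20% of the drift, and nearer 6% at month 54 if Part 1 enrolled quickly and correlation decays with time. For a drift of 0.25 to 0.3 SD that is of the order of one standard error at the last visits. No document shows that such a drift exists, so it should not be said that the late contrasts do reflect recruitment period. The primary analysis, the key secondary analyses and all formal inference are unaffected.

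**What to change.** In the SAP 7.2 mixed model, add `<trial part>*visit` to the listed terms. This removes the expected error and brings the model closer to the part-stratified Cox models. Add `baseline*visit` in the same edit as a standard precision refinement, not as a correction for mixing between parts. The platelet and neutrophil repeated-measures models in SAP 7.4.4 and 7.4.5 list randomization plan in place of trial part, also without a visit interaction, and could be aligned.

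The cost is one line of code, settled before unblinding, with no extra data and almost no loss of precision.
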